6.2.1 Race

Where more than one race category has been selected for a participant, these race categories will be combined into a single category labeled “Multiple Race” in the summary tables. The listings will reflect the original selected categories.

6.2.2 Baseline

Baseline for safety parameters as well as for exploratory parameters is defined as the last non-missing value (either scheduled, unscheduled or repeat) before the participant receives first Study Injection.

6.2.3 Duration / Study Day / Time

Study day will be calculated as the number of days from first Study Injection.

- date of event – date of first Study Injection + 1, for events on or after first Study Injection
- date of event – date of first Study Injection, for events before first Study Injection

Duration of ALS diagnosis will be presented in months and calculated as (Date of Screening – Date of Onset of Symptoms) / 30.4375.

Time to tracheostomy will be calculated as time from date of first Study Injection to date of first occurrence of ALSFRS-R questionnaire with answer “**0 - Invasive mechanical ventilation by intubation or tracheostomy**” to question “**12. Respiratory insufficiency**” presented in days.

Time to all-cause mortality will be calculated as period from date of first Study Drug Injection to date of death within 180 days presented in days.

Both time-to-event endpoints will be censored by date of last visit.

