#### **2.2.6.1. Phase 1/2 Study in Participants with Amyotrophic Lateral Sclerosis**

A Phase 1/2, open label, single center study in 18 Participants diagnosed with clinically definite, clinically probable, or clinically probable-laboratory supported ALS (VMALS-001; NCT02039401) lasting 9 months was completed. Prior to injections on Day 0, Participants were assessed using the Revised Amyotrophic Lateral Sclerosis Functional Rating Scale (ALSFRS-R), the Medical Research Council (MRC) scale for muscle strength testing, dynamometry, forced vital capacity (FVC), and muscle circumference.

All Participants (18 Participants) received a total of 64 mg of VM202 IM in the upper limbs (abductor pollicis brevis, first dorsal interosseous, biceps, deltoid, extensor carpi radialis, flexor carpi ulnaris, and flexor carpi radialis) and lower limbs (quadriceps, gastrocnemius, and tibialis anterior).

Engensis was administered over the course of four visits: Days 0, 7, 14, and 30. As in previous Engensis studies, the final dose of VM202 for each target muscle group was divided and administered 2 weeks apart with injection of the upper limbs at separate visits from injection of the lower limbs.

Post-injection, ALSFRS-R, FVC, and muscle strength (as determined by the MRC scale) were assessed at Days 30, 60, and 90, and at 6 and 9 months. Muscle circumference and dynamometry were conducted on Days 60 and 90, and at 6 and 9 months. Participants were contacted through 36 months by phone to assess survival.

[figure not shown]
After Engensis or Placebo injections through Day 30, seventeen (17) Participants completed the 9-month follow-up; one Participant died prior to the 9-month visit. Three (3) Participants completed the study (36-month follow-up), while 14 Participants died following the 9-month visit; all deceased Participants died due to respiratory failure associated with ALS. Four additional serious adverse events (SAEs) that required hospitalization were reported. All deaths and SAEs were classified as unrelated to the study drug. Injection site reactions were limited to pain and/or bruising.

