**7.3. Lost to Follow-up**

A Participant will be considered lost to follow-up if he or she repeatedly fails to return for scheduled Visits and is unable to be contacted by the Site by Day 180 (+7 days).

The following actions must be taken and recorded if a Participant fails to return to the clinic for a required study Visit:

- The site must attempt to contact the Participant and reschedule the missed Visit as soon as possible. The site must counsel the Participant on the importance of maintaining the assigned Visit schedule and ascertain whether or not the Participant wishes to and/or should continue in the study.
- If no response is obtained from the Participant, the Investigator is encouraged to contact one of the Participant's relatives or his/her general practitioner.
- Before a Participant is deemed lost to follow up, the Investigator or designee must make every effort to regain contact with the Participant, including at least three telephone calls and, finally, a certified letter to the Participant's last known mailing address. These contact attempts should be documented in the source records.
- Should the Participant continue to be unreachable, the Participant will be considered lost to follow-up.

---

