6.15.7 Time to tracheostomy

Time to tracheostomy will be presented with descriptive statistics and corresponding survival curves using Kaplan- Meier analysis (Table 14.6.8, Listing 16.2.9.8). The questionnaire is planned to be filled at Screening, Day 0 pre-dose, Day 30, Day 60 pre-dose, Day 84, Day 120 pre-dose, Day 144 and Day 180.

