6.15.8 Time to all-cause mortality

Time to all-cause mortality will be presented with descriptive statistics and corresponding survival curves using Kaplan-Meier analysis (Table 14.6.9, Listing 16.2.9.8).

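### Kaplan-Meier for time to tracheostomy censors deaths, and the mortality endpoint has an ambiguous censoring rule and no vital-status check to Day 180 for participants who leave early

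*SAP*

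**What the plan says.** SAP 6.2.3 defines both events and then censors them together.

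- **Mortality.** The time is the "period from date of first Study Drug Injection to date of death within 180 days presented in days". Nothing limits this to deaths before withdrawal.
- **Tracheostomy.** "Time to tracheostomy will be calculated as time from date of first Study Injection to date of first occurrence of ALSFRS-R questionnaire with answer", the answer being a score of 0 on item 12. Death is not part of the event.
- **Censoring.** "Both time-to-event endpoints will be censored by date of last visit".

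On the estimator, SAP 6.15.7 says: "Time to tracheostomy will be presented with descriptive statistics and corresponding survival curves using Kaplan- Meier analysis". SAP 6.15.8 says: "Time to all-cause mortality will be presented with descriptive statistics and corresponding survival curves using Kaplan-Meier analysis". Neither section mentions a competing event, a cumulative incidence or a composite with death. SAP 6.1.2 and 6.15 place both endpoints in the ITT Population, meaning everyone randomized. The mortality endpoint in Protocol sections 3 and 9.3.2 runs to Day 180.

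On follow-up, Protocol 7.1 keeps a participant who only stops study drug in the study, if the participant agrees. Protocol 7.2 offers those who leave an early-termination visit where possible, and no later contact. Protocol 7.3 covers people who miss visits: the site "must make every effort to regain contact with the Participant, including at least three telephone calls and, finally, a certified letter". Under Protocol 8.5.1, investigators need not look for events once participation has ended, and must report a death they learn of later only if they consider it at least possibly related.

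**The concern.** There are two separate problems.

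For tracheostomy, Kaplan-Meier treats a censored person as still able to have the event later. That is wrong for someone who has died. One minus the Kaplan-Meier estimate then describes tracheostomy in a population where nobody dies, and it exceeds the proportion who actually have the procedure. Conversely, an arm with deaths and no tracheostomies shows a flat, event-free curve.

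For mortality, the analysis should account for every randomized participant up to Day 180. The plan does not secure that for people who leave early, and its censoring sentence leaves the handling of a late but known death to the programmer. With so few deaths expected, one death handled either way could be the whole mortality result.

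**Working it through.** The plan attaches no event count, power or dropout rate to these endpoints, so there is no figure to reproduce. The calculations below give scale; the event patterns are assumed.

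**Inputs.** 18 participants, 12 Engensis and 6 Placebo (Protocol 5.3). One death among 18 before the 9-month visit of the earlier ALS study (Protocol 2.2.6.1). Median survival of 3 to 5 years from diagnosis (Protocol 2.2.1).

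**1. Tracheostomy.** Take an arm of n with k deaths, then one tracheostomy, and everyone else followed to Day 180.

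- Deaths censored: 1 − KM = 1/(n − k).
- Death as a competing event: cumulative incidence = [(n − k)/n] × [1/(n − k)] = 1/n.
- Tracheostomy or death: (k + 1)/n.

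| n | k | 1 − KM | Cumulative incidence | Tracheostomy or death |
|---|---|---|---|---|
| 12 | 1 | 1/11 = 9.1% | 1/12 = 8.3% | 2/12 = 16.7% |
| 12 | 2 | 1/10 = 10.0% | 1/12 = 8.3% | 3/12 = 25.0% |
| 6 | 1 | 1/5 = 20.0% | 1/6 = 16.7% | 2/6 = 33.3% |
| 6 | 2 | 1/4 = 25.0% | 1/6 = 16.7% | 3/6 = 50.0% |

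If no tracheostomy follows the death, the first two measures agree.

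**2. Mortality: which deaths are at risk of being lost.**

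- A death between visits of someone still in the study is an event at its own date.
- A known death after the last visit but within 180 days is an event under the definition. A literal reading of the censoring sentence would censor it. The SAP does not settle this.
- A death that nobody learns of after the participant has left is censored on either reading. Changing the censoring date alone does not recover it.

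The third case depends on data collection. Besides Protocol 7.2 and 8.5.1, Protocol 10.2.3 gives death from disease progression as an example of an event that cannot be an SAE. Section 8.5.9 reads more broadly. SAE forms are therefore not a sure source of dates of death.

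**3. Expected deaths by Day 180, constant hazard assumed.**

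- Time ratio: 180/(9 × 30.4375) = 0.657.
- From the earlier study: 1 − (17/18)^0.657 = 3.69%; × 18 = 0.66.
- Exact 95% limits on 1/18 are 0.14% and 27.3% over 9 months. Over 180 days these become 0.09% and 18.9%; × 18 = 0.02 and 3.4.
- From median survival of m years: 1 − 0.5^[(180/365.25)/m]. For m = 5 this is 6.6%, or 1.2 deaths; for m = 3 it is 10.8%, or 1.9 deaths.
- Chance of at least one death among 18: 0.49, 0.71 and 0.87 for the three point rates (3.69%, 6.6%, 10.8%).

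**4. Effect of one lost death.** Suppose one participant leaves after the Day 84 visit, dies on Day 120, and the rest of the arm is complete. With the death censored, Day 180 survival is 100% in either arm. With it counted, survival is 11/12 = 91.7% (Engensis) or 5/6 = 83.3% (Placebo). The shifts are 8.3 and 16.7 points.

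**The case against.** The strongest reply concerns mortality. SAP 6.2.3 counts any death dated within 180 days, and a censoring rule is ordinarily read as applying to participants without the event. A reader might infer that the last-visit rule itself discards deaths after withdrawal. On the ordinary reading it does not. What remains is an unclear sentence and a gap in data collection.

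A reader might also infer that people leave as they decline, so that the censoring is informative and biases one arm. The documents give no dropout rate and no support for that. In the earlier ALS study, 17 of 18 completed 9 months and the other participant died. Protocol 7.1 also keeps follow-up going after study drug is stopped. Nor can the contact attempts in Protocol 7.3 be taken to supply vital status after withdrawal: they apply to missed visits, and withdrawal falls under 7.2.

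On size, the swings in the working are conditional. Placebo's share of the 0.66 expected deaths is 6/18 × 0.66 = 0.22, and a lost death also requires early departure and no record (or censoring of a recorded death). No tracheostomy rate is given, and the gap with one prior death in six is 20.0 − 16.7 = 3.3 points on a single event. Listing 16.2.9.8 shows both endpoints by participant, so a reader of 18 records can see who died without a tracheostomy.

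All of this stands and limits the severity. It does not answer the tracheostomy point, because the table and curve would still report the wrong quantity. Nor does it supply a vital-status check or settle how a known late death is handled.

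**Conclusion.** The tracheostomy point holds. The event definition, the censoring rule and Kaplan-Meier together overstate incidence whenever a tracheostomy follows a death in the same arm: 20.0% against 16.7% for one prior death in six, and 9.1% against 8.3% for one in twelve.

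The mortality point holds in a limited form. The SAP is ambiguous about a known death after the last visit, and neither document secures vital status to Day 180 for participants who leave early. On a constant hazard, about 0.7 deaths are expected (0.02 to 3.4), or 1.2 to 1.9 from the protocol's median survival. Each one lost shifts its arm by about 8.3 or 16.7 points, assuming the arm is otherwise complete. The documents do not support a claim that the rule discards known deaths by design, or that it biases a particular arm.

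Severity is low: both endpoints are exploratory and descriptive, and the primary safety analysis does not depend on this rule.

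**What to change.** 1. **Tracheostomy (SAP 6.2.3, 6.15.7).** Report cumulative incidence with death as a competing event, beside the existing listing. A composite of tracheostomy or death could be added.
2. **Mortality event (SAP 6.2.3).** State that any death dated within 180 days of first injection is an event, even if it falls after the last visit.
3. **Vital status (protocol).** Ascertain Day 180 vital status for all randomized participants where consent allows, and record the date last known alive.
4. **Mortality censoring (SAP 6.2.3).** Censor participants without a death at the earlier of date last known alive and Day 180.

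Items 1, 2 and 4 cost a few SAP sentences and little programming. Item 3 costs a few telephone calls and a small change to protocol and consent wording, because contact after withdrawal is not now provided for. The method is feasible: in the earlier ALS study, "Participants were contacted through 36 months by phone to assess survival". Sample size and design are unaffected.

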6.2.4 Conventions for Missing and Partial Dates

All rules explained below for partial / missing dates will be followed unless contradicted by any other data recorded on the electronic Case Report Form (eCRF).

QMD Ref: Worldwide-TMP-ST-005-7.0 Effective: 12Aug2019	Governing QMD: Worldwide-SOP-ST-001
Confidentiality Statement	

This document is the property of Worldwide Clinical Trials Inc. and may not be duplicated, copied, altered or removed from company without prior approval from Worldwide Quality Assurance or in compliance with Worldwide Standard Operating Procedures.

Worldwide Clinical Trials Controlled Quality Management Document			
 WORLDWIDE CLINICAL TRIALS	Sponsor:	Helixmith Co., Ltd.	
Protocol Number:			VMALS-002-2
STATISTICAL ANALYSIS PLAN VERSION 3.0			

All dates presented in the individual participant listings will be as recorded on the eCRF (i.e., not completed as per the below rules).

6.2.5 Missing / Partial Start / Stop Date of Adverse Events (AE) and Concomitant Medications

Missing and partial start and stop date will be imputed for analysis purposes as follows.

Partial or missing stop date will be imputed as follows:

If the stop date is completely missing and the event has resolved, or the participant has stopped taking the concomitant medication, the stop date will be imputed as the date of the participant's last clinic visit in the study.

- If only the year is known, the stop date will be imputed as “31-Dec” of that year or as the date of the participant's last clinic visit in the study if in the same year.
- If the month and year are known, the stop date will be imputed as the last day of that month unless the stop date corresponds to the same month as the participant's last clinic visit in which case the date of participant's last clinic visit in the study will be used instead.

Missing start date will be imputed as follows:

- If the stop date occurs on or after the start of study drug or the event / concomitant medication is ongoing, the start date will be imputed as the date of the first dose of study drug.
- If the stop date occurs before the start of study drug, the start date of the event / concomitant medication will be imputed as the participant's screening date or the stop date of the event / concomitant medication whichever the earlier.

Partial start date (year present, but month and day missing)

- If the stop date occurs on or after the start of study drug or the event / concomitant medication is ongoing, and the year is the same as the year of first dosing the start date will be imputed as “01-Jan” of the same year or the date of the first dose of study drug whichever is latest. If the year is different from the year of first dosing “01-Jan” will be used.
- If the stop date occurs before the start of study drug, the start date of the event / concomitant medication will be imputed as the “01-Jan” of the same year.

Partial start date (month and year present, but day missing)

- If the stop date occurs on or after the start of study drug or the event / concomitant medication is ongoing, the start date will be imputed as the first day of the same month and

QMD Ref: Worldwide-TMP-ST-005-7.0 Effective: 12Aug2019	Governing QMD: Worldwide-SOP-ST-001
Confidentiality Statement	

This document is the property of Worldwide Clinical Trials Inc. and may not be duplicated, copied, altered or removed from company without prior approval from Worldwide Quality Assurance or in compliance with Worldwide Standard Operating Procedures.

Worldwide Clinical Trials Controlled Quality Management Document		
 WORLDWIDE CLINICAL TRIALS	Sponsor: Protocol Number:	Helixmith Co., Ltd. VMALS-002-2
STATISTICAL ANALYSIS PLAN VERSION 3.0		

year unless this partial start date is in same month as the first dose of study drug in which case the date of first dose of study drug will be used.

- If the stop date occurs before the start of study drug, the start date will be imputed as the first day of the month and year of the partial stop date.

If the start time is missing it will be imputed only in the case where the start date of the concomitant medication / event corresponds to the date of the first dose of study drug. The time will be imputed as the same time as the first dose of study drug. In all other cases the time will not be imputed.

6.2.6 Missing Last Dates of Study Drug Dosing

Not applicable in this SAP.

6.2.7 Missing Diagnosis Dates

If the month and year are present but the day is missing, the diagnosis date will be set to first day of the relevant month. If only the year is recorded the diagnosis date will be set as “01-Jan” for that year.

6.2.8 Exposure to Study Drug

Exposure to study drug will be presented as the following:

- Number of performed injections for each performed dosing visit and overall
- Total dose(mg) received, only for Engensis group, calculated as number of performed injections * 0.25 mg.
- Time of study drug exposure calculated as the date of study discontinuation or the date of End of Study (whichever comes first) minus date of first day of injections + 1.

6.2.9 Compliance

Compliance will be calculated as $100\% * [\text{volume of administered injections}] / [\text{volume of planned injections}]$. Volumes of planned injections are:

- Each anatomic area for dosing day:
 - Abductor pollicis brevis, right: 1 mL
 - 2 Abductor pollicis brevis, left: 1 mL
 - 3 First dorsal interosseous, right: 1 mL
 - 4 First dorsal interosseous, left: 1 mL
 - 5 Biceps, right: 4 mL
 - 6 Biceps, left: 4 mL

QMD Ref: Worldwide-TMP-ST-005-7.0 Effective: 12Aug2019	Governing QMD: Worldwide-SOP-ST-001
Confidentiality Statement	

This document is the property of Worldwide Clinical Trials Inc. and may not be duplicated, copied, altered or removed from company without prior approval from Worldwide Quality Assurance or in compliance with Worldwide Standard Operating Procedures.

Worldwide Clinical Trials Controlled Quality Management Document			
 WORLDWIDE CLINICAL TRIALS	Sponsor:	Helixmith Co., Ltd.	
	Protocol Number:	VMALS-002-2	
STATISTICAL ANALYSIS PLAN VERSION 3.0			

- 7 Deltoid, right: 4 mL
- 8 Deltoid, left: 4 mL
- 9 Extensor carpi radialis, right: 1 mL
- 10 Extensor carpi radialis, left: 1 mL
- 11 Flexor carpi ulnaris, right: 1 mL
- 12 Flexor carpi ulnaris, left: 1 mL
- 13 Flexor carpi radialis, right: 1 mL
- 14 Flexor carpi radialis, left: 1 mL
- 15 Quadriceps, right: 10 mL
- 16 Quadriceps, left: 10 mL
- 17 Gastrocnemius, right: 6 mL
- 18 Gastrocnemius, left: 6 mL
- 19 Tibialis anterior, right: 6 mL
- 20 Tibialis anterior, left: 6 mL
- Each side for each dosing day: 32 mL
- Each dosing day: 64 mL
- Each anatomic area for treatment cycle:
 - Abductor pollicis brevis, right: 2 mL
 - 2 Abductor pollicis brevis, left: 2 mL
 - 3 First dorsal interosseous, right: 2 mL
 - 4 First dorsal interosseous, left: 2 mL
 - 5 Biceps, right: 8 mL
 - 6 Biceps, left: 8 mL
 - 7 Deltoid, right: 8 mL
 - 8 Deltoid, left: 8 mL
 - 9 Extensor carpi radialis, right: 2 mL
 - 10 Extensor carpi radialis, left: 2 mL
 - 11 Flexor carpi ulnaris, right: 2 mL
 - 12 Flexor carpi ulnaris, left: 2 mL
 - 13 Flexor carpi radialis, right: 2 mL
 - 14 Flexor carpi radialis, left: 2 mL
 - 15 Quadriceps, right: 20 mL
 - 16 Quadriceps, left: 20 mL
 - 17 Gastrocnemius, right: 12 mL

QMD Ref: Worldwide-TMP-ST-005-7.0 Effective: 12Aug2019	Governing QMD: Worldwide-SOP-ST-001
Confidentiality Statement	

This document is the property of Worldwide Clinical Trials Inc. and may not be duplicated, copied, altered or removed from company without prior approval from Worldwide Quality Assurance or in compliance with Worldwide Standard Operating Procedures.

Worldwide Clinical Trials Controlled Quality Management Document			
 WORLDWIDE CLINICAL TRIALS	Sponsor:	Helixmith Co., Ltd.	
	Protocol Number:	VMALS-002-2	
STATISTICAL ANALYSIS PLAN VERSION 3.0			

- 18 Gastrocnemius, left: 12 mL
 - 19 Tibialis anterior, right: 12 mL
 - 20 Tibialis anterior, left: 12 mL
- Each side for treatment cycle: 64 mL
- Each treatment cycle: 128 mL
- Each anatomic area for whole study:
 - Abductor pollicis brevis, right: 6 mL
 - 2 Abductor pollicis brevis, left: 6 mL
 - 3 First dorsal interosseous, right: 6 mL
 - 4 First dorsal interosseous, left: 6 mL
 - 5 Biceps, right: 24 mL
 - 6 Biceps, left: 24 mL
 - 7 Deltoid, right: 24 mL
 - 8 Deltoid, left: 24 mL
 - 9 Extensor carpi radialis, right: 6 mL
 - 10 Extensor carpi radialis, left: 6 mL
 - 11 Flexor carpi ulnaris, right: 6 mL
 - 12 Flexor carpi ulnaris, left: 6 mL
 - 13 Flexor carpi radialis, right: 6 mL
 - 14 Flexor carpi radialis, left: 6 mL
 - 15 Quadriceps, right: 60 mL
 - 16 Quadriceps, left: 60 mL
 - 17 Gastrocnemius, right: 36 mL
 - 18 Gastrocnemius, left: 36 mL
 - 19 Tibialis anterior, right: 36 mL
 - 20 Tibialis anterior, left: 36 mL
- Each side for whole study: 192 mL
- Whole study: 384 mL.

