**Table 1: Injection and Dosing Schedule: Treatment Cycle 1: Days 0 and 14**

Anatomic Target Area	Number of Injections (Engensis or Placebo) and Dose per Treatment Cycle					
	Treatment Cycle 1: Day 0		Treatment Cycle 1: Day 14		Total per Treatment Cycle	
	Right	Left	Right	Left		
Number of Injections (Engensis or Placebo) 1 injection = 0.5 mL						
Hands						
Abductor pollicis brevis	2 injections	2 injections	2 injections	2 injections	8 injections	
First dorsal interosseous	2 injections	2 injections	2 injections	2 injections	8 injections	
Upper Arms						
Biceps	8 injections	8 injections	8 injections	8 injections	32 injections	
Deltoid	8 injections	8 injections	8 injections	8 injections	32 injections	
Lower Arms						
Extensor carpi radialis	2 injections	2 injections	2 injections	2 injections	8 injections	
Flexor carpi ulnaris	2 injections	2 injections	2 injections	2 injections	8 injections	
Flexor carpi radialis	2 injections	2 injections	2 injections	2 injections	8 injections	
Legs						
Quadriceps	20 injections	20 injections	20 injections	20 injections	80 injections	
Gastrocnemius	12 injections	12 injections	12 injections	12 injections	48 injections	
Tibialis anterior	6 injections	6 injections	6 injections	6 injections	24 injections	
Total Number of Engensis or Placebo Injections	64 injections	64 injections	64 injections	64 injections	256 injections	
Engensis Dose per Treatment Day/Cycle	32 mg		32 mg		64 mg	

#### 4.1.1.2. Treatment Cycle 2

Participants will receive Engensis or Placebo by IM injections to the right and left sides of the specified muscles on Days 60 and 74 as shown in [Table 2](#).

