6.10 Treatment Compliance

Treatment compliance will be presented for the Safety Analysis Population.

Descriptive statistics for each side separately and total at each treatment day and treatment cycle as well as for whole study, as described in Section 6.2.9, will be presented by treatment group (Table 14.3.5.4).

Values of treatment compliance will be presented in listing (Listing 16.2.10.3).

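### SAP 6.2.9 sets tibialis anterior planned volumes at twice what the protocol's injection counts imply, so its area volumes do not add up to its own side totals

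*SAP*

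**What the plan says.** SAP 6.2.9 defines compliance as administered volume divided by planned volume, times 100%. It lists planned volumes for each muscle and side, for each side, and for both sides together, at three levels: dosing day, treatment cycle and whole study.

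- **Dosing day:** "Tibialis anterior, right: 6 mL", with a side total given as "Each side for each dosing day: 32 mL".
- **Treatment cycle:** "Tibialis anterior, right: 12 mL", with a side total given as "Each side for treatment cycle: 64 mL".
- **Whole study:** "Tibialis anterior, right: 36 mL", with a side total given as "Each side for whole study: 192 mL".

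The left-side entries are the same as the right.

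Protocol Tables 1, 2 and 3 each schedule 6 tibialis anterior injections per side per dosing day, 24 per cycle over both sides and both days, and state that "1 injection = 0.5 mL".

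SAP 6.10 announces "Descriptive statistics for each side separately and total at each treatment day and treatment cycle as well as for whole study", and sends individual compliance values to Listing 16.2.10.3 without saying whether they go down to the muscle.

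**The concern.** Six injections of 0.5 mL make 3 mL, not 6 mL. The tibialis anterior entries equal the gastrocnemius entries at every level, although the protocol schedules 12 injections per side per dosing day for gastrocnemius and 6 for tibialis anterior. The SAP's area list also cannot be squared with its own side totals.

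These figures are operative because SAP 6.2.9 makes them denominators. A denominator that is twice too large halves the ratio, so a participant who received every scheduled injection would look half-treated in one muscle. A programmer who built the side denominator by adding up the area list, instead of taking the stated side total, would carry the error into the side and overall figures as well.

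**Working it through.** **Inputs.** Volume per injection: 0.5 mL (Protocol Tables 1 to 3). Injections per side per dosing day (same tables): abductor pollicis brevis 2, first dorsal interosseous 2, biceps 8, deltoid 8, extensor carpi radialis 2, flexor carpi ulnaris 2, flexor carpi radialis 2, quadriceps 20, gastrocnemius 12, tibialis anterior 6. There are two dosing days per cycle and three cycles, hence six dosing days. Area volumes and totals: SAP 6.2.9.

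**Step 1: the SAP's side totals reproduce from the protocol counts.**

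- Day: 2+2+8+8+2+2+2+20+12+6 = 64 injections; 64 × 0.5 = 32 mL per side.
- Cycle: 32 × 2 = 64 mL per side.
- Study: 32 × 6 = 192 mL per side.
- Both sides: 64, 128 and 384 mL. The last agrees with the 768 injections in Protocol 4.4.2: 768 × 0.5 = 384 mL.

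**Step 2: the SAP's area volumes do not sum to those totals.** Per side:

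- Day: 1+1+4+4+1+1+1+10+6 = 29 for the other nine muscles; 29 + 6 = 35 mL.
- Cycle: 2+2+8+8+2+2+2+20+12 = 58; 58 + 12 = 70 mL.
- Study: 6+6+24+24+6+6+6+60+36 = 174; 174 + 36 = 210 mL.

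**Step 3: locate the excess.** The other nine muscles match protocol count × 0.5 mL at all three levels. Tibialis anterior does not: 6 × 0.5 = 3 mL per day, 3 × 2 = 6 mL per cycle, 3 × 6 = 18 mL for the study.

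| Level (per side) | Tibialis anterior, SAP | Tibialis anterior, from protocol | Sum of SAP areas | SAP side total | Excess |
|---|---|---|---|---|---|
| Dosing day | 6 mL | 3 mL | 35 mL | 32 mL | 3 mL |
| Cycle | 12 mL | 6 mL | 70 mL | 64 mL | 6 mL |
| Study | 36 mL | 18 mL | 210 mL | 192 mL | 18 mL |

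The excess equals the tibialis anterior difference at each level (6 − 3, 12 − 6, 36 − 18). With 3, 6 and 18 mL in place, the areas sum to 29 + 3 = 32, 58 + 6 = 64 and 174 + 18 = 192 mL, and every stated total is recovered.

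**Step 4: effect on compliance.**

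- Tibialis anterior at full dosing: 3/6 = 6/12 = 18/36 = 50%.
- Tibialis anterior on one dosing day with one of six injections missed: 2.5/6 = 41.7%, against 2.5/3 = 83.3%.
- Side or overall at full dosing, stated totals as denominators: 32/32 = 64/64 = 192/192 = 100%.
- Side or overall at full dosing, summed area volumes as denominators: 32/35 = 64/70 = 192/210 = 91.4%.

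**The case against.** The best defence is that no announced table uses the wrong numbers. SAP 6.10 summarises compliance by side and in total, and the denominators stated for those levels all agree with the protocol. The output list in SAP section 11 has no compliance table by muscle. The 50% figure appears only if Listing 16.2.10.3, or some added output, goes down to the muscle. If it did, other outputs would expose it: SAP 6.9 reports performed injections by anatomic area and side, and section 11 plans a listing of missed injections, so a reader would see six injections given, none missed, and 50% compliance. The 91.4% figure would require a programmer to ignore totals that the SAP states outright.

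All of this stands, and it limits the consequence. It does not remove the error. SAP 6.2.9 defines a denominator for each anatomic area, and SAP 6.10 does not rule out area-level values in the listing. That another output would reveal the mistake is a reason to correct it before programming.

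Two other explanations fail. A text-extraction fault would not produce six entries that scale consistently (6, 12, 36) on both sides. A deliberate departure from the protocol is not declared: SAP section 9 reports no changes to the planned analysis.

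**Conclusion.** The concern holds and is minor. Six entries in SAP 6.2.9 (right and left, at three levels) are exactly twice the volumes implied by Protocol Tables 1 to 3, and they make the area list exceed the SAP's own side totals by 3, 6 and 18 mL. As written, the area-level rule gives 50% compliance for tibialis anterior at full dosing.

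The reach is narrow. Side, day, cycle and study compliance under SAP 6.10 is unaffected provided the stated totals are the denominators. Total dose comes from the count of performed injections (SAP 6.2.8). Neither the ITT nor the Safety Analysis Population depends on compliance (SAP 6.1.2, 6.1.3), and no endpoint does. The arithmetic uses only figures in the two documents. The one open point is whether any output will show compliance by muscle; the table and listing shells are not in the documents, so this cannot be settled from them. The finding concerns an analysis denominator and passes no judgement on the dose.

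**What to change.** Before compliance is programmed, reconcile the six tibialis anterior entries in SAP 6.2.9 with Protocol Tables 1 to 3 and with the SAP's own totals. The test is that the ten area volumes per side sum to 32 mL per dosing day, 64 mL per cycle and 192 mL for the study. It would also help to state in SAP 6.10 whether Listing 16.2.10.3 carries area-level values, and that side and overall compliance use the stated totals.

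The cost is six numbers and, if wanted, a sentence or two in the SAP. No change to the protocol or to data collection is needed.
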